- 5. Known allergies to nickel, gold or other components of stainless steel.

Study Duration

The duration will be up to 5 visits over the course of approximately 2 weeks. Study sessions will be limited to 90 minutes in length. A subject can elect to have up to two sessions per day which would reduce the duration of the study. We are requiring that at least one parent or caregiver be present for all study visits.

Study Procedures

Screening and Enrollment

The study will be explained to the potential candidates and their parents, including the purpose, procedures, expectations for participation, benefits, and risks. Upon request, an IRB approved patient information sheet explaining the study can be provided for review at home. If the potential subject shows interest in the study, additional pre-screening questionnaires will be administered to determine eligibility. Specifically, our study coordinator will review the inclusion and exclusion criteria over the telephone. We have included this paradigm successfully in other studies with the Brainport, which reduces the likelihood that a subject will travel to our site at their own expense but not meet our inclusion and exclusion criteria.

If the potential subject has successfully passed our pre-screen tests over the phone, then he or she will be provided by mail with the Informed Consent form and the HIPAA Research Authorization Form, the participant Assent form and the Parental Permission form, which will have been approved by the University of Pittsburgh Institutional Review Board. We will offer to provide a JAWS compatible version and/or an audio version to the subject prior to their arrival so that they can review it at their own pace and with their families. These same documents will be reviewed again with the subject and their family member upon arrival for the initial visit. In the event that the subject is not able to sign their own name, a proxy designated by the subject may provide the signature.

A HIPAA research authorization will allow the researchers to access the subject's medical records related to their diagnoses and to enable further disclosure of the subject's study data to the study personnel, study monitor, clinical research organization, and the IRB.

Overview of Study Design

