Following consent, subjects will complete baseline psychophysical assessments which have been used in similar BrainPort studies. These consist of simple and easy to understand computer based tests of the ability to detect light, direction, motion, and letters. In addition, we may administer seated tests where the subject is asked to recognize objects, pictures or depth cues. Each of these tests takes between 5 and 15 minutes to complete.

Following baseline studies, a structured "Clinical Training Phase" with the will occur. Our lab has trained over 100 subjects to use the BrainPort device (largest center worldwide), and has established the methods to provide core skill acquisition under the direction of an occupational therapist who works in our laboratory (refer to attachment). Because the subjects in this study will not be taking the device home, but will be restricted to limited use in the controlled laboratory setting, the training will not have to involve outdoor navigation or more advanced skills. After the Brainport training phase has been completed, and the subject has demonstrated basic proficiency with the device, the same set of outcomes assessments administered at baseline will be repeated.

If at any point during the study, the subject subsequently does not meet inclusion criteria or satisfies exclusion criteria, or wishes to stop participation, further testing will be discontinued and the subject will be dismissed.

Detailed description of study design by visit:

Session 1:

- Informed consent
- Review of inclusion and exclusion criteria
- Baseline medical and medication history
- Oral exam
- Baseline psychophysical assessments

Session 2, 3, & 4:

- Training session
- Oral exam

Session 5:

- Repeat outcomes assessments with Brainport
- Oral exam

Each session is expected to last 90 minutes, will be performed at the UPMC, and will be performed by the Research Staff and/or PI.

Note: follow up visits can be combined into a single longer day with morning and afternoon sessions at the request of the subject. We are allowing this because subjects and their families are responsible for their own travel, lodging and meal expenses.

Evaluation Procedures/Outcomes Assessments (Detailed descriptions):

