Potential subjects will be examined to verify that vision in each eye is light perception or worse by the PI according to standard practices at the UPMC Eye Center. Subjects will not need to be dilated. In most cases, our blind subjects have prosthetic eyes or have such badly damaged eyes that verification of blindness by clinical exam does not need to occur. In these instances, the ocular examination will be waived. Inspection of the oral cavity, medical and medication history will be performed.

Psychophysical assessments: We begin with rudimentary vision assessment such as light perception and proceed to increasingly complex visual tasks which approach "normal" vision as the device allows. In the event that a subject is not able to perceive better than light perception, tests which ascertain higher functions will not be administered. Below is a representative description of the tests that we commonly employ with BrainPort studies.

The Basic Assessment of Light Motion (BaLM) and Basic Assessment of Grating Acuity (BaGA) have been developed with the intent of testing artificial vision devices, which provide the most rudimentary visual precepts. They have been used to quantify such qualities as light detection, temporal resolution and light motion as well as "grating acuity" for situations where standard resolution acuity is nonexistent. The methods for testing have been described in Artificial Vision by Mark Humayan. Both tests run on a software platform and are presented on a computer LCD screen to the subject. The stimuli they present consist mainly of large targets of varying patterns. The subject is seated in a regular chair while looking at a computer display for these non-invasive tests, each of which last an average of 10 minutes or less. The subject is able to stop the test in the event they feel they need to get up and move around. All visual acuity measurements will be performed by a single examiner. For baseline testing, while one eye is tested, the other will be occluded. We use this to make sure that both eyes have visual acuity of LP or worse to meet entry criteria. Subsequent testing using the Brainport is done using the camera pointed at the computer screen. All vision tests will be performed in a room with standardized illumination.

BaLM Test

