Upon starting the first subtest the program runs self-paced, requiring the patient to enter an alternative choice response via a numeric keypad. Most visually impaired subjects are familiar with a numeric keypad. At the beginning of each test there is a short sound to prompt a patient's response. After the patient has pressed the corresponding key, two different sounds are played to indicate either a right or a wrong response. Hit rates and stimulation patterns (frequency of sine wave grating, orientation and contrast) are recorded.

Analysis of Test Results

The BaLM and BaGA tests automatically calculate percentages of correct responses of each test, as well as mean reaction times and standard deviation of measurements for each test. ANOVA analyses will be completed to compare pre- Brainport and post- Brainport use. Analysis will also be completed to compare performance between those with acquired versus congenital blindness, age, gender and presence of TBI.

Object Recognition Tasks

Object recognition tasks which involve the subject seated at a desk will be undertaken. These tests will involve tasks that will first ask the subject whether an object is present or not (2 choice discrimination). If successful, then the more complex discrimination tasks will be employed, which will ask the subject to recognize a specific object out of a choice of 3 objects or 5 objects. Testing will be repeated for 20 trials each.

Analysis of Test Results

All data is recorded into a password protected PASW database. Primary performances measure the ability to detect whether an object is or is not present, as well as to recognize a specific object within a field of other objects. Secondary measures include time to object recognition. ANOVA analysis will be completed to compare pre-Brainpor and post-Brainport use. Additional analysis will compare performance between those with congenital versus acquired blindness, age, gender and presence of TBI.

ADVERSE EVENTS

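### The 2-choice gate leaves few children with an unaided baseline on the 3- and 5-choice object tasks, although specific-object recognition is a primary pre/post measure

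*Combined protocol and SAP*

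**What the plan says.** - **Primary Efficacy Endpoints** and **Statistical analysis (general)**: object recognition is one of four primary areas. Each is judged as improvement over the child's own baseline, with t-tests before and after training on every measure.
- **Subject selection criteria** and **Inclusion Criteria**: 8 children, all with light perception or worse in both eyes.
- **Object Recognition Tasks**: the tasks are definite, "Object recognition tasks which involve the subject seated at a desk will be undertaken". They start with a 2-choice task (is an object present or not). The 3- and 5-choice tasks are conditional: "If successful, then the more complex discrimination tasks will be employed". Each task has 20 trials. Success is not defined.
- **Analysis of Test Results**, under the same section: the primary performance measures are detecting presence "as well as to recognize a specific object within a field of other objects". Then "ANOVA analysis will be completed to compare pre-Brainpor and post-Brainport use".
- **Overview of Study Design**: at baseline "we may administer seated tests where the subject is asked to recognize objects, pictures or depth cues". After training, the battery given at baseline is the one repeated.
- **Evaluation Procedures/Outcomes Assessments**, Psychophysical assessments paragraph: "In the event that a subject is not able to perceive better than light perception, tests which ascertain higher functions will not be administered".

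No section says whether the gate is applied separately at each time point, or how a level that was not given is scored.

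**The concern.** A within-child comparison needs a score at both times. The gate decides who receives the 3- and 5-choice tasks by performance on the 2-choice task. Without the device, children at light perception or worse can be expected to score near chance on that task; the protocol itself notes that most of its blind subjects have prosthetic or badly damaged eyes. Following the rule as written would therefore withhold the harder levels from most children at baseline.

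What happens at Session 5 depends on a point the plan leaves open. If the battery repeated is strictly the one given at baseline, the harder levels are not given again and the measure is lost. If the gate is run afresh with the device, Session 5 scores come mainly from children who succeed with it and have no baseline. Their average would describe the successful children, not all 8. Neither outcome can be repaired once the data are collected.

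**Working it through.** **The plan's own figure.** The protocol claims power above 0.8 with 8 children at p<0.05. It gives no effect size, standard deviation or test, so this cannot be reproduced. Working backwards, a paired t-test with 8 pairs at two-sided 0.05 has 80% power at a standardized paired difference of 1.16. At that same difference, 2 pairs give about 10% power, and fewer than 2 pairs allow no test.

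**Step 1: who gets past the gate unaided.** From the plan: 20 trials, 2 choices, 8 children. Assumed: the pass mark r, and guessing at p = 0.5.

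P(pass) = Σ C(20,k) 0.5^20 for k = r to 20; expected passers = 8 × P; P(at least 2 of 8) = 1 − (1−P)^8 − 8P(1−P)^7.

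| Assumed mark | P(pass) | Expected of 8 | P(at least 2) |
|---|---|---|---|
| 15/20 | 0.0207 | 0.17 | 1.1% |
| 14/20 | 0.0577 | 0.46 | 7.4% |
| 13/20 | 0.1316 | 1.05 | 28% |
| 12/20 | 0.2517 | 2.0 | 64% |

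15/20 is the lowest mark significantly above chance at one-sided 5%.

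**Step 2: sensitivity to residual vision.** Assume four children guess and four have 70% accuracy on the presence task, which gives them pass probabilities of 0.416, 0.608 and 0.772 at marks 15, 14 and 13.

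- Mark 15: 4 × 0.0207 + 4 × 0.416 = 1.7 expected; P(at least 2) = 58%.
- Mark 14: 4 × 0.0577 + 4 × 0.608 = 2.7; 86%.
- Mark 13: 4 × 0.1316 + 4 × 0.772 = 3.6; 98%.

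**Step 3: Session 5, only if the gate is re-run with the device.** At an assumed 80% 2-choice accuracy, the pass probabilities are 0.804, 0.913 and 0.968 at marks 15, 14 and 13, so 6.4, 7.3 or 7.7 of 8 reach the 3-choice task. If all guessed at baseline, nearly all these scores are unpaired.

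To size the selection, assume learners know the answer on 60% of trials and guess otherwise (2-choice 0.6 + 0.4/2 = 0.80; 3-choice 0.6 + 0.4/3 = 0.733), while the rest guess. At mark 15 with 4 learners:

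- Passers = 4 × 0.804 + 4 × 0.0207 = 3.30.
- Their mean = (3.22 × 0.733 + 0.083 × 0.333)/3.30 = 72.3%, which is 39 points above chance.
- The mean over all 8 = (4 × 0.733 + 4 × 0.333)/8 = 53.3%, which is 20 points above chance.

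With 2 learners the figures are 37 against 10 points; with 6, 40 against 30.

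**Step 4: what ungated testing would give.** Same model, 8 pairs, 20 trials per child at each time, 3-choice task, paired t-test, 200,000 simulated trials. The Bonferroni level is assumed to be 0.05/4 = 0.0125, one test per primary area, since the plan does not give the number of tests.

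| Learners of 8 | Power, two-sided 0.05 | Power, two-sided 0.0125 |
|---|---|---|
| 2 | 8% | 1% |
| 4 | 43% | 11% |
| 6 | 94% | 64% |

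**The case against.** **A stepped test is a reasonable choice.** It spares a young blind child 40 trials of guessing. That stands as a reason for having a gate. It does not explain how a gated level can also be a primary pre/post measure with no rule for children who were stopped.

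**The loss depends on assumptions.** It does. At a lax mark of 12/20, two guessers are expected to pass, and children with useful residual detection pass more often (step 2). The claim is therefore that few children would have a baseline, not that none would.

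**The selection figures may never arise.** If only the baseline battery is repeated, step 3 does not apply. That stands, but on that reading the measure disappears for most children.

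**Chance is a good enough baseline.** If unaided children truly guess, comparing Session 5 with chance is more powerful under the same model: 53% against 43% with 4 learners and 99.7% against 94% with 6, at 0.05. This makes it a sound fallback. It still needs every child to be given the level at Session 5, and it would credit the device with any unaided performance above chance.

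**Stronger readings.** A reader might infer that the stop rule contradicts the Object Recognition Tasks section, or that object recognition has no baseline at all. The documents do not support either:

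- The stop rule sits in the paragraph on psychophysical tests, which speaks of progressing as far as the device permits, so it may concern device-aided testing.
- The Overview introduces seated object tests as additional to the computer tests, and the risks section names psychophysical and object recognition testing separately.
- The FrACT acuity exclusion shows that not every test is barred at entry.
- The 2-choice task comes first and is ungated.

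With the optional wording in the Overview, this is ambiguity about unaided object testing, not a demonstrated conflict.

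**Conclusion.** The concern holds for one primary sub-measure: recognizing a specific object at the 3- and 5-choice levels. Under the gate, the expected number of children with such a baseline is 0.17 to 2.0 of 8 if all guess (marks 15 down to 12), and 1.7 to 3.6 if four have 70% accuracy (marks 15 down to 13). The pass marks and accuracies are assumptions, because the plan gives none. The planned paired test on this measure is then impossible or rests on a handful of children.

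The whole primary analysis is not at risk. The 2-choice score has a baseline under the Object Recognition Tasks section, the gate does not affect the other primary areas, and the endpoint counts improvement in any area. The change is worth making because it is cheap. It should not be expected to deliver a well-powered test: with 8 pairs, power is low under the assumed model unless most children learn, and lower still after Bonferroni correction.

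**What to change.** State that neither the stop rule in the Psychophysical assessments paragraph nor the success gate applies to the object recognition tasks. Give every child the same 2-, 3- and 5-choice tasks, 20 trials each, without the device at baseline and with it at Session 5. For the remaining tests, such as gratings and letters, say at which time points the stop rule applies.

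If a level cannot be given at baseline, pre-specify a one-sample comparison of Session 5 scores from all children with chance (33% or 20%). Label it as having no measured baseline, and never enter 0% for a test that was not given.

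The cost is a wording change plus 2 × 20 = 40 extra trials, mostly guessed, at each time point for a child the gate would have stopped. At baseline it is 3 × 20 = 60 if object tests would otherwise be skipped. The Overview says "Each of these tests takes between 5 and 15 minutes to complete". The 60 baseline trials therefore take 5 to 15 minutes if the object task is one test, or 3 × 5 = 15 to 3 × 15 = 45 minutes if each level is one. Because "Study sessions will be limited to 90 minutes in length" and the other Session 1 items are not timed, some children may have to finish at the start of Session 2, before first using the device, which takes time from training.

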We will recruit 8 blind subjects between the ages of 7 and 18 from the UPMC Eye Center patient population, the Wicab website, the established volunteer list of over 200 blind subjects from the Sensory Substitution Laboratory, the Clinical Trials Registry at the University of Pittsburgh and the patient population at the ophthalmology department at the UPMC Children's Hospital. Recruitment of normally sighted controls is not justified. We expect to screen 15 blind subjects to achieve our enrollment target. Based upon estimates from our preliminary data, this sample size should allow us to show differences between the naïve and BrainPort condition with a significance level of p<0.05 and a power of greater than 0.8.

We will attempt to enroll an equal number of males and females to the extent this is possible. We will attempt to enroll minority populations in our study.

Inclusion Criteria

Volunteer subjects enrolled and treated in this study must meet all of the following criteria:

- 1. Between the age of 7 and 18
- 2. Blind (documented visual acuity of light perception or worse) in both eyes from an eye care provider.
- 3. Able to read (or have read to him or her), understand and sign the Informed Consent and Assent form.
- 4. Able to understand the training and rehabilitation protocols involved in the study.
- 5. Willing to use the BrainPort device

Exclusion Criteria

Subjects will be excluded from the study if they meet any of the following criteria:

- 1. Current oral health problems as determined by the subject's history, and an examination of the oral cavity performed by a member of the study team. Subject is excluded if any of the following conditions are met:
 - a. A history of injury to the tongue resulting in impaired sensation or use of the tongue.
 - b. Visible open lesions, cold sores, abrasions, blisters, or rash on the tongue.
 - c. Oral surgery or dental work in the past 3 months or anticipated to occur for the duration of participation in the study (does not include routine dental health exams/cleanings).
 - d. Piercing on the tongue.
 - e. Performance better than 20/5000 on the FrACT acuity test (same visual criteria as FDA safety study).
- 2. Known neuropathies of tongue or skin tactile system.
- 3. Unwilling or unable to adhere to all study requirements, including completion of the training period, evaluation tests and follow up visits.
- 4. Implanted electrical medical devices such as pacemakers.

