Investigators will assess subjects for adverse events during each training session and each follow-up visit. Oral exams will be performed at baseline, and at the end of each session. Subjects will also be asked at each visit whether they have experienced any medical problems since their last visit and whether or not they would consider the problems to be due to the device use. All expected and unexpected untoward occurrences related to the Brainport will be considered adverse events and will be reported to the PI, and the reviewing IRB as soon as possible but no later than 10 days following the occurrence. Subjects will be instructed to report any suspected adverse event to the research staff immediately.

Potential adverse events that will be monitored for with the BrainPortTM vision device include the following:

- A mild tingling sensation or residual sensation in the region of the electrical stimulus on the tongue. While unusual, this sensation is not reported to be annoying, does not interfere with normal activities, and it fades with time.
- Discomfort associated with the electrical stimulus on the tongue. No observed or received reports of tongue irritation or pain occurred during a one year long FDA safety study in 75 subjects. Although no long-term adverse events are known or expected, no data is available on the long-term effects of electrical stimulation of the tongue.

Investigators will be asked to report and evaluate all adverse events and indicate the probable relationship to the device. All adverse events will be followed until they are resolved or the investigator has determined the condition to be chronic or stable or the subject's participation in the study has been terminated.

ETHICAL CONSIDERATIONS

Risks and Mitigation Strategies

There are no foreseeable risks involved in the proposed psychophysical and object recognition testing for visual function as these involve looking at a computer monitor or other objects while seated.

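### At Sessions 2–5 no oral exam is scheduled between arrival and device placement, so a new, unreported tongue lesion may not be caught until after that session's stimulation

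*Combined protocol and SAP*

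**What the plan says.** The Adverse Events section gives the exam timing: "Oral exams will be performed at baseline, and at the end of each session". The visit-by-visit description under Overview of Study Design lists an oral exam at all five sessions without a clock time. At Sessions 2–4 it comes after the training entry, and at Session 5 after the repeat outcome tests with the device.

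Exclusion criterion 1 concerns oral health problems "as determined by the subject's history, and an examination of the oral cavity performed by a member of the study team". Item 1b under it reads "Visible open lesions, cold sores, abrasions, blisters, or rash on the tongue". Overview of Study Design carries the criteria through the whole study: "If at any point during the study, the subject subsequently does not meet inclusion criteria or satisfies exclusion criteria", then "further testing will be discontinued and the subject will be dismissed".

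Three other provisions bear on the point. The Adverse Events section has staff assess for adverse events in each session, ask at each visit about health problems since the last one, and instruct subjects to report suspected events at once. Study Duration adds "We are requiring that at least one parent or caregiver be present for all study visits". It also allows pairing: "A subject can elect to have up to two sessions per day which would reduce the duration of the study".

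**The concern.** Criterion 1b is a visible sign that the protocol itself identifies partly by looking. The rule that stops a subject who meets an exclusion says what to do once a lesion is known, but it does not provide for a look at the moment when the look would prevent exposure. A child who develops a sore between sessions, and who neither feels nor mentions it, could receive a full session of tongue stimulation that the protocol's own rule would forbid. These children have light perception at best and cannot see their own tongues.

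Attribution of adverse events is a lesser issue. Investigators must judge how likely an event is to be related to the device. With exams only at session ends, the onset of an unreported lesion can be placed no more precisely than between two session ends. An arrival reading would separate onset between sessions from onset during a session.

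**Working it through.** The main check is the order of procedures. The protocol states no figure to reproduce.

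1. **Exam timing.** The order of entries in the visit list would not by itself fix when the exam happens. The Adverse Events section does: baseline, then session end.
2. **Other oral inspections.** The examination under Exclusion Criteria and the inspection under Evaluation Procedures both belong to screening and eligibility. Neither is scheduled on arrival at a later session.
3. **Device sessions.** Sessions 2, 3, 4 and 5 use the device; Session 1 is consent and baseline testing. Scheduled exams between arrival and placement: 0 of 4.
4. **What the previous exam covers.** Every placement follows the previous session's exam (for Session 2, the one at Session 1). The uncovered lesions are those that arise after it.
5. **Length of the gap.** Five visits over about 14 days leave 4 gaps, or 14 / 4 = 3.5 days each if evenly spaced (an assumption). Paired sessions shorten some gaps to hours.
6. **Number of arrivals.** 8 children × 4 sessions = 32 at most. Of these, 8 × 3 = 24 (75%) follow earlier stimulation, so a lesion seen on arrival may still be a delayed device effect.

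**Frequency, illustration only.** The documents give neither input. Let *r* be the chance of a new visible lesion per gap (assumed 0.5% to 5%) and *u* the share that go unreported (assumed 10% to 50%). Expected number = 32*ru*; chance of at least one = 1 − (1 − *ru*)^32.

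| r | u | Expected | At least one |
|---|---|---|---|
| 0.5% | 10% | 0.016 | 1.6% |
| 0.5% | 50% | 0.08 | 7.7% |
| 5% | 10% | 0.16 | 14.8% |
| 5% | 50% | 0.80 | 55.5% |

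If every family pairs sessions (5 sessions in 3 days, so 2 overnight gaps × 8 = 16) and same-day gaps produce no lesion, 16*ru* is 0.008 to 0.40, and the chance of at least one is 0.8% to 33.3%.

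**Comparison with the present plan.** At Sessions 2–4, a lesion present on arrival would usually still be visible at that session's end exam, and the current rule would then dismiss the child. An arrival look brings that finding forward and spares one exposure; it does not create the loss. Only at Session 5 does the present schedule collect the outcome before the exam. There the expected number of children affected is 8*ru* = 0.004 to 0.20 on the same assumed rates.

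**The case against.** The strongest reply is that little is left uncovered. Each session ends with an exam, the health question is asked at every visit, subjects are told to report problems at once, a caregiver attends, and staff may see a lesion when fitting the device. What remains is a visible lesion that nobody noticed or mentioned, found at most one 90-minute session late. This stands, and it is why the point is minor. It does not close the gap: the question and the reporting instruction rely on self-report, the question is not timed before placement, and the in-session assessment is not described as a look in the mouth.

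A second reply is that no harm is shown. The background gives 11.85 μJ per pulse against a stated limit of 300 mJ, a ratio of 300,000 / 11.85 ≈ 25,000. The child sets the strength and can remove the device, and the Adverse Events section reports no tongue irritation or pain among 75 subjects in a one-year safety study. This also stands, with the limit that none of it is said to concern tongues with lesions. Criterion 1b shows that the protocol wants such children kept off the device.

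A reader might infer that a new lesion will be missed, or that the trial exposes children to real danger. The documents support neither. They show that no exam is scheduled on arrival, so a lesion may not be caught; staff who notice or hear of one must still stop.

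**Conclusion.** The gap is real and small. Followed exactly, the plan could stimulate a child whom its own exclusion rule bars, for one session, if the lesion is new since the last exam and unreported. Expected harm is low, and no efficacy conclusion depends on it.

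The frequency is unknown. The span from about 2% to 56% in the illustration comes wholly from assumed rates; its upper end is the two highest assumptions multiplied together. A reader might take it as evidence that such an event is likely, and it is not. The case for the change rests on the schedule and on how little the change costs.

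The gain for attribution is modest. An arrival reading narrows the onset window but cannot show that a lesion is unrelated to the device.

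**What to change.** In the visit description under Overview of Study Design and in Adverse Events, add for Sessions 2–5:

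- on arrival, before placement, existing staff briefly inspect the tongue for the 1b items and record present or absent;
- the existing question about medical problems is asked at the same moment;
- if a lesion is present, the device is not placed that day;
- the end-of-session exam stays.

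The cost is short text additions and a minute or two per session by staff who already do oral exams. The main new cost is a possible delayed or lost Session 5 outcome; one child is 1/8 = 12.5% of the sample. An occasional hold for a harmless mark should also be expected, and a return visit is a burden because "subjects and their families are responsible for their own travel, lodging and meal expenses".

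Whether a transient lesion should lead to postponement rather than dismissal is a separate, optional choice for the investigator. The present text provides only for dismissal, so postponement would need its own line.

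### Adverse events are defined as device-related occurrences only, although investigators must then rate device relationship for all adverse events, so harm first thought unrelated may go unreported

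*Combined protocol and SAP*

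**What the plan says.** Everything on this point that defines or rates events is in the protocol section ADVERSE EVENTS.

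- **Definition:** "All expected and unexpected untoward occurrences related to the Brainport will be considered adverse events". No other definition appears in the document.
- **Reporting, in the same sentence:** these occurrences "will be reported to the PI, and the reviewing IRB as soon as possible but no later than 10 days following the occurrence".
- **Solicitation:** "Subjects will also be asked at each visit whether they have experienced any medical problems since their last visit". The sentence goes on to ask "whether or not they would consider the problems to be due to the device use".
- **Spontaneous reports:** "Subjects will be instructed to report any suspected adverse event to the research staff immediately".
- **Examination:** "Oral exams will be performed at baseline, and at the end of each session".
- **Causality rating:** "Investigators will be asked to report and evaluate all adverse events and indicate the probable relationship to the device".
- **Follow-up:** adverse events are followed until they resolve, are judged chronic or stable, or the subject's participation ends.

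STUDY MONITORING adds that the investigators meet at least every eight weeks, with adverse events and unanticipated problems among the topics. The planned sample, under Subject selection criteria, is small: "We will recruit 8 blind subjects between the ages of 7 and 18".

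**The concern.** A causality rating is informative only if the events put to it include some that the device may not have caused. Here the definition has already restricted the set to related occurrences. Either the rating has little left to decide, or the definition does not mean what it says.

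What is at stake is the class of problems that look unrelated at first contact and later prove not to be. Risks and Mitigation Strategies lists several harms open to more than one explanation, such as falls, collisions, tooth injury and irritation of the mouth. It also accepts that unknown side effects may exist. An unknown effect is the kind most easily set aside when relatedness is tested first. There is no control group whose background event rate could show such an error, and if a problem was not recorded it cannot be reclassified later.

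**Working it through.** The plan gives no adverse event rate, expected count or safety analysis, so there is no figure to reproduce. The check is a comparison of the plan's own sentences.

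1. **What counts as an adverse event.** Under the definition, an untoward occurrence qualifies only if it is related to the BrainPort. It does not matter whether it was expected.

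2. **What the rating assumes.** The later sentence covers all adverse events and asks for the likely relationship to the device. That presupposes a set in which relationship is still open. Under step 1 it is not, because a relatedness judgement has already been made.

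3. **Who makes the first judgement.** The plan does not say. The later rating is given to investigators. The subject, aged 7 to 18, is asked for an opinion on cause when the problem is elicited. The visit description allows sessions to be run by research staff, the PI or both.

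4. **What depends on the definition.** Follow-up to resolution, the 10-day PI and IRB report, and the adverse event item at investigator meetings all apply to adverse events. A problem first judged unrelated is outside all three, unless it is raised at a meeting as an unanticipated problem.

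5. **What does not depend on it.** The question about medical problems at each visit is open as to cause, and the oral examination at the end of each session needs no attribution. Information is therefore gathered before relatedness is judged. Whether it is kept once judged unrelated is not stated.

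6. **Size.** Let *m* be the share of truly device-related problems that are first judged unrelated. The count of device-related adverse events under the literal definition is then (1 − *m*) × the true count. The document gives no value for *m*. It can lie anywhere from 0 (no loss) to 1 (complete loss), so no estimate is possible.

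7. **Procedures other than the device.** Session 1 includes baseline psychophysical testing, before training with the device begins in Session 2. An untoward occurrence caused by that testing would not meet the definition. An observation window that opens at first device use would miss it too.

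**The case against.** The strongest reply is that this is loose drafting and that the safety net is wider than the definition. Investigators assess at every training session and follow-up visit, subjects are asked about any medical problem, and the mouth is examined each session. The definition shares a sentence with the 10-day rule, so it may have been meant only as the criterion for reporting to the IRB. A broad screen for possible relatedness followed by a graded judgement would also be coherent. Exposure is short: up to 5 visits over about 2 weeks, sessions of at most 90 minutes, a parent or caregiver present, and no home use. The foreseeable harms are already named as device risks and so are less likely to be dismissed.

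Much of this stands, and it limits the point in three ways.

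- A reader might infer that events judged unrelated are never recorded and that safety is in fact under-counted. The document does not say so. It solicits problems of any cause and is silent on what is retained, and the case report forms are not part of it.
- A reader might infer that a child's denial removes an event. The relationship rating belongs to investigators, and the child's view is one item asked.
- A reader might measure the effect by the sample size: one child in 8 is 1/8 = 12.5%, and 0 of 8 has an exact one-sided 95% upper bound of 1 − 0.05^(1/8) = 31.2%. Both figures follow from having 8 subjects and hold under any definition. They do not measure this defect, and the plan names no safety rate for it to distort.

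The reply does not remove the conflict. The sentence is worded as a definition, it is the only one, and later steps rely on it. If it was meant as a reporting criterion, the plan has no definition of an adverse event at all, and the same amendment is needed. Oral examinations cover only the mouth, and asking about a problem does not ensure that it is followed up or reported.

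**Conclusion.** The point holds as a conflict between two stated rules. Adverse events are limited to device-related occurrences, yet relationship to the device is to be rated for all of them. On a literal reading, problems first thought unrelated escape adverse event follow-up, reporting and review, so device-related harm may be under-reported. This is a risk and not a demonstrated loss. Its size cannot be derived, and it rests on two assumptions that the document neither confirms nor excludes: that staff apply the definition as written, and that problems judged unrelated are not retained elsewhere. The efficacy analysis is not affected. The correction is worth making because it is cheap and because unrecorded events cannot be recovered afterwards.

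**What to change.** Amend ADVERSE EVENTS as follows.

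1. Define an adverse event as any untoward medical occurrence from the first study procedure to the last scheduled session (Session 5), whether or not it is related to the device.
2. Record every problem that is solicited, volunteered or observed. The subject's opinion on cause may be noted but does not decide whether the problem is kept.
3. Have the investigator rate relationship to the device after the event is recorded.
4. State the existing 10-day PI and IRB rule in its own sentence, applying to events judged related.
5. Report counts of all adverse events and of related adverse events.

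The cost is a one-paragraph amendment and a few more case report form lines for about 8 children. No endpoint, device procedure or visit changes.
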